8.2 Secondary Study Endpoints

The secondary outcome will be the surgeon's intraoperative findings during brachial plexus reconstructive microsurgery. Specifically, agreement between MRI and intraoperative findings, with respect to the level(s) and extent of injury of each nerve root and the location of root injury (pre- vs. post-ganglionic) will be determined.

AMS and Toronto scores will be evaluated at 12, 18 and 30 months of age, which will correlate roughly with 6, 12, and 24 months post-operatively for those infants who undergo surgery.

8.3 Sample Size Determination and Power/Accrual Rate

The sample size was calculated based on the primary aim which is to determine the discriminant ability of the SRS system to discern infants requiring surgical intervention and those who will recover spontaneously, based on the area under the receiver operating characteristic (ROC) curve. To prove that the SRS has the discriminant ability to effectively identify surgical patients, we would like to demonstrate an area under the curve (AUC) of at least 0.90. Assuming an expected surgical rate of 30% and a null AUC of 0.75, 70 subjects would be required to achieve 80% power with a type I error of 5%. Table 2 indicates the variations in sample size calculation if the true surgical rate is higher or lower than 30%. This demonstrates that there is little variation in the number of necessary surgical subjects given various surgical rate scenarios. Obtaining at least 21 surgical subjects would provide greater than 80% power to test for an AUC of at least 0.90. Thus, the assumption of a 30% rate with an enrollment of 70 evaluable patients should be sufficient to meet the goals of the study.

During the 1-year time frame of our pilot study, we identified 16 subjects that met eligibility criteria. Of these, 3 families declined participation, and 4 infants were not able to complete the MRI scan. As our technique of positioning the infant improved over the pilot study, we believe a higher percentage of infants will be able to complete the MRI scan successfully going forward. There is a similar volume of BPBP patients at our two institutions, such that we expect approximately 15 subjects per year will be eligible to participate at each site, with 10 per year at each site likely to consent and complete the MRI scan successfully. Thus, we will plan to enroll patients for the first 3.5 years of the study and expect to yield 105 eligible participants. Assuming that 85% of eligible infant's consent and at least 75% have adequate MRI scans, it will be possible to obtain the required sample size. A third site has been included to help guard against poorer than expected accrual and to provide for more generalizable results.

Table 2. Sample size required to detect an AUC of 0.90 with 80% power.

| Surgical rate | Number of surgical subjects | Number of non-surgical subjects | Total number of subjects |
|---------------|-----------------------------|---------------------------------|--------------------------|
| 25% | 21 | 66 | 82 |
| 30% | 21 | 51 | 70 |
| 35% | 22 | 41 | 63 |
| 40% | 23 | 34 | 57 |

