2.1 Objectives

2.1.1 Primary Objective

Verify whether non-sedated 3D volumetric structural magnetic resonance imaging (MRI) obtained ≥ 28 days and ≤ 4 months old can reliably discriminate between brachial plexus birth palsy (BPBP) injury patients who require surgical reconstruction versus those who will recover spontaneously.

2.1.1.1 Hypothesis:

The SRS will effectively be able to discriminate between infants who require surgical reconstruction versus those who will recover spontaneously.

2.1.2 Secondary Objective 1:

Assess whether MRI findings for pre-operative planning in infants with BPBP, specifically the level(s) and extent of injury of each nerve root and the location of root injury (pre- vs. post-ganglionic), correlate with intraoperative findings identified during brachial plexus reconstructive microsurgery.

2.1.2.1 Hypothesis:

MRI findings for pre-operative infants will exhibit characteristics similar to those found intraoperatively.

2.1.3 Secondary Objective 2:

Two standard BPBP clinical measures – the Active Movement Scale (AMS) and Toronto scores will be used to confirm clinical outcomes of our decision-making both for and against surgery.

2.1.3.1 Hypothesis:

AMS and Toronto scores will improve to functional levels at final follow-up for those subjects who were determined not to need surgery. AMS and Toronto scores will improve following surgical intervention for those subjects who undergo surgery.

3.0 Subject Selection:

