Each subject's MRI scan will be reviewed independently by neuroradiologist investigators. The neuroradiologists will interpret the MRI scan and report their findings in the medical record as per standard clinical protocols. Surgeons and families will be aware of these findings and will be able to view the images. However, the SRS calculation will be performed outside the medical record and will not be available to surgeons until after data collection is completed in order to minimize bias. Our pilot data demonstrated inter-rater reliability (Krippendorff's alpha) of 0.78 for calculation of the SRS. The neuroradiologist investigators at the other study centers will read and calculate SRS scores for the pilot study subjects with the goal of exceeding an inter-rater reliability of 0.75 with the other neuroradiologists prior to testing study subjects. In addition, during the study period, a subset of MRI scans will be de-identified and shared between institutions for the purposes of inter-observer and intra-observer analysis. Figure 1 illustrates the calculation of the SRS score from the MRI findings. Each injured level is first assigned 1 point, with additional points assigned for pre-ganglionic injuries: 2 points for each absent nerve rootlet, 2 points for each pseudomeningocele, 0.5 points for each abnormal nerve rootlet; and for post-ganglionic injuries: 1.5 points for each neuroma and 0.5 points for each abnormal nerve. If the zone of injury includes both the pre- and post-ganglionic regions, only the pre-ganglionic injury is scored. The total radiologic score ranges from 0 points (no evidence of nerve root injury on MRI) to 25 points (all 5 levels with pre-ganglionic pseudomeningoceles and absent nerve rootlets). In addition, the neuroradiologist will score each nerve root level as intact, post-ganglionic rupture, or pre-ganglionic avulsion. This information will then be compared with the findings at surgery as described above for those infants who undergo surgery.

Figure 1. Calculation of the Shriners Radiological Score (SRS)

4.3.2.1 Subjects who do not complete the scan or end up with unusable images can repeat the MRI up to two additional times as long as they are within the eligibility window.

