8.4 Statistical Methods

The primary analysis for this will be assessing the discriminant ability of the SRS system to distinguish patients who do versus do not go on to surgery, by estimating the area under the receiver operating characteristic (ROC) curve with a 95% confidence interval. In addition, an optimal cutoff value for the SRS will be identified using Youden's Index which maximizes the sum of sensitivity and specificity. Sensitivity and specificity will be estimated to help quantify the utility of the SRS system to discern between surgical patient groups. The area under the ROC curve (AUC) for the SRS system may be compared to the AUC for the AMS, currently part of clinical surgical decision making, to assess whether the MRI score offers a comparable, earlier detection method for the need for surgical intervention. Secondary analysis will include comparing MRI nerve root findings at each nerve root level (C5, C6, C7, C8, and T1) with intraoperative root findings in surgical patients. Weighted kappa coefficients along with 95% confidence intervals will be estimated to assess the concordance in detecting intact, ruptured, or avulsed roots between MRI and intraoperative inspection. In addition, inter- and intra-rater reliability of the SRS will be assessed by estimating Krippendorff's alpha along with a 95% confidence interval. The AMS and Toronto evaluations at 18 and 30 months of age in the non-operative group will be used to confirm that these patients do achieve spontaneous recovery, and will be compared with the scores for the surgery group at the same time points.

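### Section 8.3 claims power to show an AUC of at least 0.90, but its null is 0.75; Section 8.4 ties its 95% interval to neither value

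*Combined protocol and SAP*

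**What the plan says.** Section 8.3 sets the goal for the Shriners Radiological Score (SRS): "we would like to demonstrate an area under the curve (AUC) of at least 0.90". The next sentence gives the design values: "Assuming an expected surgical rate of 30% and a null AUC of 0.75", and then "70 subjects would be required to achieve 80% power with a type I error of 5" per cent. It does not say whether the 5% is one- or two-sided, and it names no variance formula or test. The section goes on to claim that "Obtaining at least 21 surgical subjects would provide greater than 80% power to test for an AUC of at least 0.90". The caption of Table 2 reads "Sample size required to detect an AUC of 0.90 with 80% power".

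Section 8.4 describes the primary analysis as assessing discrimination "by estimating the area under the receiver operating characteristic (ROC) curve with a 95% confidence interval". It gives no null value, interval method or success rule. The hypothesis in Section 2.1.1.1 has no number either: "The SRS will effectively be able to discriminate between infants who require surgical reconstruction versus those who will recover spontaneously".

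**The concern.** Two AUC values play different roles in Section 8.3, and the text blurs them. A study sized against 0.75 can rule out 0.75 when the truth is 0.90. It gives no assurance of establishing 0.90, although 0.90 is what the goal and the power sentence name.

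The analysis section does not settle the matter. Suppose the observed AUC is 0.87. With the Hanley-McNeil standard error at 21/49 (0.0531), the 95% interval is 0.87 ± 1.96 × 0.0531 = 0.766 to 0.974. That is a success against 0.75 and not a demonstration of 0.90, and the plan does not say which reading governs. The interval method also remains open, so both the chance of success and the error rate could depend on a choice made after the data are seen.

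**Working it through.** **Inputs from Section 8.3.** Null A0 = 0.75, assumed truth A1 = 0.90, type I error 5%, power 80%, and 70 evaluable infants at a 30% surgical rate, so n1 = 0.30 × 70 = 21 and n0 = 49.

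**1. The plan's own figure.** No method is named, so I tried common ones. The Hanley-McNeil variance is

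V(A) = [A(1−A) + (n1−1)(Q1−A²) + (n0−1)(Q2−A²)] / (n1·n0), with Q1 = A/(2−A) and Q2 = 2A²/(1+A).

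At 21/49, SE(0.75) = 0.0683 and SE(0.90) = 0.0473. One-sided 5% power is

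Φ[(0.15 − 1.645 × 0.0683)/0.0473] = Φ(0.80) = 0.79.

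The binormal (Obuchowski) variance on the logit scale uses a difference of ln 9 − ln 3 = 1.099 and SE divided by A(1−A). It gives one-sided power of 0.80.

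| Surgical rate | 25% | 30% | 35% | 40% |
|---|---|---|---|---|
| Table 2 total | 82 | 70 | 63 | 57 |
| Hanley-McNeil, one-sided 5% | 84 | 72 | 65 | 59 |
| Binormal logit, one-sided 5% | 80 | 70 | 63 | 59 |

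Both come within 2 infants in every row. The 70 is thus consistent with a one-sided 5% test of 0.75. This is an inference from the totals only: in two rows of Table 2 the components do not add to the total (21 + 66 = 87 against 82; 21 + 51 = 72 against 70).

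**2. What 21/49 delivers for 0.90.** I simulated 40,000 trials per setting with normal scores and a true AUC of 0.90. With equal spread in the two groups:

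- the point estimate is at least 0.90 in about 53% of trials;
- the 95% lower limit exceeds 0.90 in 2.8% (logit-DeLong) or 9.4% (untransformed DeLong).

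With Hanley-McNeil Wald limits, an observed AUC of about 0.96 is needed to put the lower limit above 0.90.

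**3. What a 95% limit delivers for 0.75.** The lower end of a two-sided 95% interval works at one-sided 2.5%, not 5%. The intervals compared are:

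- untransformed DeLong: Â ± 1.96·SE, with the empirical DeLong SE;
- logit-DeLong: logit(Â) ± 1.96·SE/[Â(1−Â)], transformed back;
- Hanley-McNeil Wald: Â ± 1.96·√V(Â).

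Each cell gives power at a true AUC of 0.90, then one-sided error at a true AUC of 0.75. Spread is the surgical SD divided by the non-surgical SD.

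| Rule: lower limit above 0.75 | Spread 1 | Spread 1.5 | Spread 0.5 |
|---|---|---|---|
| Logit-DeLong 95% | 77% / 2.4% | 64% / 2.4% | 86% / 2.0% |
| Hanley-McNeil Wald 95% | 85% / 3.5% | 83% / 5.5% | 87% / 2.3% |
| Untransformed DeLong 95% | 89% / 5.3% | 82% / 5.9% | 93% / 4.6% |
| Logit-DeLong 90% | 87% / 4.9% | 78% / 5.0% | 93% / 4.4% |

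Repeat runs differ by about one percentage point. The SRS is coarse ("The total radiologic score ranges from 0 points (no evidence of nerve root injury on MRI) to 25 points"), so tied scores were also tried: normal scores floored at 0 and capped at 25, in steps of 0.5 or 1 point, with 13% to 54% of non-surgical infants at zero. Logit-DeLong 95% then gives 74% to 78% power with 2.1% to 2.5% error.

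**The case against.** The null of 0.75 stands in the sentence straight after the stated goal, so a statistician can read the power sentence correctly in context. The Table 2 caption is ordinary wording for an alternative value. No section requires a lower limit above 0.90, so the 3% to 9% measures a criterion the plan never sets explicitly. The study will report an AUC with its interval, and any reader can hold that against 0.75.

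Most of this stands, and it limits the point. It does not rescue the wording: Section 8.3 speaks of proof, a null, power and type I error, which is a test, and Section 8.4 contains none. Nor does context supply the sidedness, the interval or the success rule. Even under the mildest reading, that the point estimate should reach 0.90, the chance is about half.

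Three stronger readings are tempting, and the documents do not support them.

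- *That 70 is an arithmetic error.* Step 1 reproduces it closely.
- *That a two-sided 5% level would need far more than 70.* The two formulas in step 1 do give 94 and 86 when made two-sided. But two-sided versions that use only the variance at 0.90, on the AUC scale, need 55 (Hanley-McNeil) or 66 (binormal), with power of 0.887 and 0.827 at 21/49. They do not match all four totals of Table 2, but with no method named they cannot be excluded.
- *That the 95% interval of Section 8.4 has only 63% power.* That figure, Φ[(0.15 − 1.96 × 0.0683)/0.0473] = 0.63, belongs to a two-sided test with the null variance, which needs an observed AUC of about 0.884. An actual Hanley-McNeil 95% limit clears 0.75 from about 0.86, which gives the 83% to 87% above.

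**Conclusion.** The point holds as a misstated power claim and a missing decision criterion, and should be fixed. The sample size stands. The 80% refers to excluding 0.75 at a true AUC of 0.90. It does not refer to showing 0.90, which a 95% lower limit would do in roughly 3% to 9% of trials at that truth.

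With a 95% limit, power to exclude 0.75 lies anywhere from about 64% to 93%, depending on the interval and the spread of scores. The higher figures come partly from intervals whose one-sided error can run to about 5% or 6% against a nominal 2.5%. A shortfall below 80% is therefore conditional on the interval chosen; it is not a fixed property of the design.

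The textual part needs no simulation. The percentages rest on 21/49 and on assumed score distributions, since the documents give none for the SRS.

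**What to change.** In Section 8.3, call 0.90 the assumed true AUC and 0.75 the value to be excluded. Reword the goal and the power sentence to match, and state the sidedness of the 5%.

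In Section 8.4, state that success means the lower limit of a pre-named interval with near-nominal error, for example logit-DeLong, exceeds 0.75. Then choose one of two routes:

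- declare one-sided 5% and use the lower limit of the 90% interval for the decision, with power of about 87% at equal spread (78% to 93% across the spreads tried), while still reporting the 95% interval; or
- keep the 95% limit for the decision and restate the power as about 77% (64% to 86%).

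The cost is a few sentences and no extra infants. The drawback is that the second route states a slightly less favourable power, and the first makes a one-sided 5% standard explicit.

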8.4 Statistical Methods

The primary analysis for this will be assessing the discriminant ability of the SRS system to distinguish patients who do versus do not go on to surgery, by estimating the area under the receiver operating characteristic (ROC) curve with a 95% confidence interval. In addition, an optimal cutoff value for the SRS will be identified using Youden's Index which maximizes the sum of sensitivity and specificity. Sensitivity and specificity will be estimated to help quantify the utility of the SRS system to discern between surgical patient groups. The area under the ROC curve (AUC) for the SRS system may be compared to the AUC for the AMS, currently part of clinical surgical decision making, to assess whether the MRI score offers a comparable, earlier detection method for the need for surgical intervention. Secondary analysis will include comparing MRI nerve root findings at each nerve root level (C5, C6, C7, C8, and T1) with intraoperative root findings in surgical patients. Weighted kappa coefficients along with 95% confidence intervals will be estimated to assess the concordance in detecting intact, ruptured, or avulsed roots between MRI and intraoperative inspection. In addition, inter- and intra-rater reliability of the SRS will be assessed by estimating Krippendorff's alpha along with a 95% confidence interval. The AMS and Toronto evaluations at 18 and 30 months of age in the non-operative group will be used to confirm that these patients do achieve spontaneous recovery, and will be compared with the scores for the surgery group at the same time points.

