We have developed a rapid (<10 minute imaging acquisition) volumetric magnetic resonance imaging (MRI) sequence with high spatial resolution and soft tissue contrast that does not require sedation or administration of a contrast agent and provides an accurate assessment of the level and severity of both pre- and post-ganglionic BPBP injuries [1]. The pilot data we acquired on 9 infants demonstrates the ability of this imaging protocol to distinguish those infants who went on to surgery at 6 months of age from those who made a spontaneous recovery. Additional study enrollment would validate the ability of imaging protocol to differentiate between operative and non-operative injuries, which would benefit both groups: first, those with injuries who do require surgery could potentially be reconstructed earlier and more accurately, and second, families of the majority of infants who will recover spontaneously could be spared months of worry. Our research goal is to recruit a total of 100 patients over a 5-year period yielding at least 70 evaluable patients at three institutions (Shriners Northern California, Boston Children's Hospital, and Gillette Children's Specialty Hospital) utilizing the same imaging, serial clinical exams, and surgical protocols as our pilot study.

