3.3 Number of Subjects
Up to 100 subjects will be enrolled from the three research sites.

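### Sensitivity and specificity are to be estimated at a Youden cutoff apparently chosen in the same infants, with no correction, so both are expected to be too high on average, mainly sensitivity

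*Combined protocol and SAP*

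**What the plan says.** Section 8.4 makes the AUC the primary analysis, "by estimating the area under the receiver operating characteristic (ROC) curve with a 95% confidence interval". It then adds an SRS cutoff identified by Youden's index, "which maximizes the sum of sensitivity and specificity. Sensitivity and specificity will be estimated to help quantify the utility of the SRS system".

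Section 4.3.2 defines the score but sets no threshold: "The total radiologic score ranges from 0 points (no evidence of nerve root injury on MRI) to 25 points". Section 1.1 cites a 9-infant pilot, and sections 4.3.2 and 7.2.1 use the pilot scans for reader reliability. No cutoff is carried forward from it. Section 4.1 describes a single prospective cohort. No section provides a split sample, cross-validation, bootstrap or external validation set. Section 8.4 plans 95% confidence intervals for the AUC, kappa and Krippendorff's alpha, but states none for sensitivity and specificity.

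On size, section 1.1 plans to "recruit a total of 100 patients over a 5-year period yielding at least 70 evaluable patients", section 3.3 says "Up to 100 subjects will be enrolled from the three research sites", and section 8.3 says "Obtaining at least 21 surgical subjects would provide greater than 80% power to test for an AUC of at least 0.90".

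**The concern.** The Youden cutoff is the one at which the sample's own sensitivity plus specificity is largest. Part of that maximum is chance: the cutoff settles where these particular infants happen to separate well. Estimates read off at that point in the same infants are therefore expected to exceed what the same cutoff achieves in new infants from the same population. The plan does not say outright that the same infants are used for both steps, but it names no other sample.

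Section 8.4 presents these two figures as the measure of how useful the score is. An overstated sensitivity means an understated share of surgical infants whom the cutoff would miss. Someone applying the published cutoff elsewhere would, on average, expect fewer missed cases than will occur.

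**Working it through.** **Inputs from the documents.** Section 8.3: surgical rate 30%, null AUC 0.75, target AUC 0.90, 70 evaluable infants, 21 of them surgical, hence 70 − 21 = 49 non-surgical. (The 30% row of Table 2 prints 51 non-surgical, which would sum to 72; the stated total of 70 is used here.) Section 3.3 caps enrolment at 100, so 30/70 is an upper bound on evaluable infants. Section 4.3.2 gives the scoring rules.

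**The plan's own figure.** Hanley-McNeil variance, with Q₁ = A/(2−A) and Q₂ = 2A²/(1+A):

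Var(A) = [A(1−A) + (n₁−1)(Q₁−A²) + (n₀−1)(Q₂−A²)] / (n₁n₀)

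- A = 0.75, 21/49: [0.1875 + 20(0.0375) + 48(0.0804)]/1029 = 0.00466, SE 0.0683.
- A = 0.90, 21/49: [0.09 + 20(0.0082) + 48(0.0426)]/1029 = 0.00224, SE 0.0473.
- Power, one-sided 5%: Φ[(0.15 − 1.645 × 0.0683)/0.0473] = Φ(0.80) = 0.788.

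Solving for 80% power gives 72 infants against the stated 70. That is close enough to confirm 21/49 as the planned size, and shows that the calculation concerns the AUC only.

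**Why sensitivity is hit harder.** One infant moves sensitivity by 1/21 = 4.8 points but specificity by only 1/49 = 2.0 points. The smaller group has the noisier curve, so the maximisation exploits it more.

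**Binormal model (assumed).** Non-surgical scores N(0,1), surgical N(d,1), with d = √2 × Φ⁻¹(0.90) = 1.812. At the true optimum, sensitivity = specificity = Φ(d/2) = 0.818. In each simulated study the Youden cutoff is chosen, and the apparent values are compared with the true values at that same cutoff. For a continuous score at 21/49, with the cutoff midway between scores:

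| | Apparent | True at chosen cutoff | Excess |
|---|---|---|---|
| Sensitivity | 0.863 | 0.798 | +6.5 points |
| Specificity | 0.841 | 0.813 | +2.7 points |

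(Differences were taken before rounding.) At 30/70 the excesses are +5.4 and +2.3. With 23/34 (the 40% row of Table 2) they are +5.8 and +3.9. At 35/35 they are about equal (+4.1 and +4.0).

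**SRS-built model (assumed).** Five root levels are each scored 0, 1, 1.5, 2.5, 3, 3.5 or 5 under section 4.3.2, driven by a latent severity calibrated to the stated AUC; one variant allows only 0, 2.5 or 5 per level. AUC 0.90, 21/49, cutoff at an observed score:

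| Assumed severity mix | Sensitivity apparent / true | Specificity apparent / true |
|---|---|---|
| Moderate | 0.859 / 0.795 | 0.836 / 0.816 |
| 34% of non-surgical infants score 0 | 0.853 / 0.792 | 0.843 / 0.823 |
| 75% score 0 | 0.847 / 0.795 | 0.875 / 0.860 |
| Three states per level, 64% score 0 | 0.836 / 0.797 | 0.856 / 0.841 |

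In misses per 100 surgical infants, that is 14 to 16 apparent against 20 to 21 true.

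**Range over AUC 0.80 to 0.95**, in points too high, sensitivity then specificity:

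| Score model | 21/49 | 30/70 |
|---|---|---|
| SRS-built | 3.4–7.7; 1.3–2.6 | 2.6–5.9; 1.1–2.2 |
| Binormal, continuous to 0.5 SD steps | 3.0–8.6; 1.4–3.2 | 2.4–6.9; 1.0–2.7 |
| Binormal, 1 SD steps (very coarse) | 1.1–3.6; 0.4–1.6 | 0.3–2.7; 0.1–1.3 |

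This is an average effect. With SRS-built scores, sensitivity was overstated in 68–82% of simulated studies at 21/49 and in 62–80% at 30/70. Both quantities were overstated together in 40–54% and 36–53%.

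**Does a correction work?** A bootstrap stratified by surgery status, re-selecting the cutoff in each resample, was applied to the moderate mix at AUC 0.90 and 21/49, with the cutoff at the midpoint between scores. Mean sensitivity was 0.859 apparent, 0.819 corrected and 0.801 true. The correction removes 0.040 of 0.058, about 69% of the bias. Over all SRS-built settings it removes 65–81% at 21/49 and 68–88% at 30/70.

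**The case against.** The strongest reply is that nothing in the plan is decided by these figures. The hypothesis, sample size and primary analysis use the AUC, no target is set for sensitivity or specificity, and surgeons are blinded to the SRS. That stands, and it limits the seriousness of the point.

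Second, the bias is smaller than the sampling error. The exact 95% interval for 18 of 21 runs from 64% to 97%, and for 26 of 30 from 69% to 96%. In the simulations such intervals around the apparent values covered the true value in about 95–99% of studies. This also stands: exact intervals plus an exploratory label would do much of the work. But the plan states neither, and an interval does not move the point estimate, which is the figure most likely to be quoted.

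Third, the bootstrap gains little accuracy. With SRS-built scores at 21/49, sensitivity RMSE falls only from 0.088–0.113 to 0.084–0.102, and specificity RMSE changes by at most 0.004. With very coarse scores RMSE is unchanged or up to 0.007 worse. The case for the correction is therefore less average bias, not much greater precision.

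Fourth, the size depends on a score distribution the documents do not give, and the emphasis on sensitivity depends on a surgical rate near 30%. Both are true. The direction did not change in any model run, and sensitivity remained the more affected at 40% surgical.

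Finally, the true values here assume new infants from the same population, judged by the same reference. That reference is a surgeon's decision which takes the MRI into account (section 8.1), so performance elsewhere depends on more than the choice of cutoff.

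**Conclusion.** The concern holds. If the plan is followed as written, sensitivity and specificity at the chosen cutoff will be too high on average. At the planned 21/49, the assumed models put the excess at about 3 to 9 points for sensitivity and 1 to 3 points for specificity, and less if the score turns out to be very coarse. Confidence is high for the direction and lower for the exact size.

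The conclusion assumes that the same infants choose the cutoff and are then scored at it, and that surgical infants are the minority. The primary AUC, its power and the care of enrolled infants are untouched. The point should be corrected, but it concerns a secondary, descriptive result.

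**What to change.** Add to section 8.4, before any analysis:

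> Sensitivity and specificity at the Youden cutoff will be reported as apparent values with exact 95% confidence intervals, and as optimism-corrected values from bootstrap resamples stratified by surgery status, with the cutoff re-selected in each resample. The cutoff is exploratory until validated in other infants.

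Cross-validation is an acceptable alternative to the bootstrap. The section should also state that the same cohort is used for choosing the cutoff and for estimating performance, or name the other sample if there is one.

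The cost is a few lines of analysis code and no additional infants or visits. Reported values will be a few points lower. Some average bias in sensitivity will remain with SRS-built scores. With very coarse scores almost none remains (−0.8 to +0.9 points), but there the correction brings no gain in RMSE.

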1.1 Background

Brachial plexus birth palsy (BPBP) affects approximately 1 in 1,000 children at birth, and though the majority of infants regain full function of the affected arm, many of these injuries result in lifelong disability. Varying degrees of BPBP, from mild (neuropraxia) to severe (post-ganglionic root rupture or pre-ganglionic root avulsion), are indistinguishable on the initial clinical exam. Serial clinical examination is the current gold standard for separating infants who will recover spontaneously from those who will need reconstructive surgery. Unfortunately, this "wait and see" period may last for up to 6 months, and the effectiveness of surgery can decrease during this time. The surgeon must balance the fact that 60-80% of infants with BPBP will recover spontaneously without surgery with the knowledge that earlier nerve repair improves outcomes for infants with more severe injuries. A non-invasive diagnostic test which differentiates these two groups of infants with BPBP within weeks of birth may help improve surgeons' prognostic accuracy and therefore the treatment of this disorder. In addition, currently surgeons rely on operative exploration, visual inspection and somewhat non-specific somatosensory evoked potentials (SSEPs) to differentiate pre-ganglionic and post-ganglionic injuries, which have completely different surgical treatments. A pre-operative test that provided accurate and specific diagnosis of each root injury would improve pre-operative planning and accuracy of treatment.

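### Secondary Objective 1 asks about pre- versus post-ganglionic location, but section 8.4 plans only one three-category weighted kappa, with unstated weights, which can be high when location is merely guessed

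*Combined protocol and SAP*

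**What the plan says.** Secondary Objective 1 (section 2.1.2) covers the level and extent of injury at each root and "the location of root injury (pre- vs. post-ganglionic"). Section 8.2 repeats that agreement on "the location of root injury (pre- vs. post-ganglionic) will be determined".

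Both sides of the comparison use the same three categories. On MRI, "the neuroradiologist will score each nerve root level as intact, post-ganglionic rupture, or pre-ganglionic avulsion" (section 4.3.2). Section 4.3.3 has the surgeon record the same three states. Among injured roots, rupture versus avulsion is therefore the location question itself.

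Section 1.1 explains why it matters: surgeons need to "differentiate pre-ganglionic and post-ganglionic injuries, which have completely different surgical treatments".

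Section 8.4 plans "comparing MRI nerve root findings at each nerve root level (C5, C6, C7, C8, and T1) with intraoperative root findings in surgical patients", and names the statistic: "Weighted kappa coefficients along with 95% confidence intervals will be estimated to assess the concordance in detecting intact, ruptured, or avulsed roots". It states no weight matrix and no benchmark. It does not say clearly whether kappa is reported per level or pooled, or how roots from the same infant are handled. It plans no rupture-versus-avulsion table, kappa, sensitivity or specificity.

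**The concern.** A single coefficient over three categories mixes two questions: is the root injured, and if so, is the injury pre- or post-ganglionic? A reader who is good at the first and has no information on the second can still obtain a respectable kappa. If the weights follow the order intact, ruptured, avulsed, calling a rupture an avulsion counts as a near miss, although the protocol's own background treats that distinction as decisive for the type of surgery.

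At stake is how the result can be read. A kappa around 0.7 could be taken as support for MRI in pre-operative planning without the location part of the objective having been examined by itself. An analysis of location added after the data are seen would be post hoc.

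**Working it through.** The plan gives no kappa value, target or precision, so there is no figure of its own to reproduce. The check asks what the planned statistic returns when location is only guessed.

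**Inputs.** Three categories, from sections 4.3.2 and 4.3.3. Weights are not stated, so unweighted, linear and quadratic are all shown, with order intact < ruptured < avulsed. The shares of intact, ruptured and avulsed roots are not in the documents; those below are assumptions. Section 8.3 expects 21 operated infants, hence 21 × 5 = 105 roots.

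**Formula.** Kappa = 1 − Σ(d × observed share) / Σ(d × share expected by chance). The penalty d is 0 or 1 (unweighted), |i−j|/2 (linear) or (|i−j|/2)² (quadratic). Confusing rupture with avulsion thus earns credit 1 − 0.5 = 0.50 (linear) or 1 − 0.25 = 0.75 (quadratic).

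**Base case.** 40% intact, 30% ruptured, 30% avulsed. MRI separates intact from injured perfectly and guesses location by coin flip. The only disagreement is rupture/avulsion, with share 0.30. Expected shares: intact/ruptured 2 × 0.4 × 0.3 = 0.24; intact/avulsed 0.24; ruptured/avulsed 2 × 0.3 × 0.3 = 0.18.

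- Unweighted: 1 − 0.30 / (0.24 + 0.24 + 0.18) = 1 − 0.30/0.66 = 0.55.
- Linear: 1 − 0.15 / (0.12 + 0.24 + 0.09) = 1 − 0.15/0.45 = 0.67.
- Quadratic: 1 − 0.075 / (0.06 + 0.24 + 0.045) = 1 − 0.075/0.345 = 0.78.
- Rupture versus avulsion alone: agreement 0.50, chance 0.50, kappa 0.

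**Varying the assumptions** (injuries split 50/50 throughout):

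| Scenario | Unweighted | Linear | Quadratic | Rupture vs avulsion kappa |
|---|---|---|---|---|
| A. 40% intact, perfect intact/injured, location guessed | 0.55 | 0.67 | 0.78 | 0 |
| B. As A, 10% intact/injured error | 0.44 | 0.53 | 0.62 | 0 |
| C. 60% intact, otherwise as A | 0.64 | 0.75 | 0.84 | 0 |
| D. 10% intact, otherwise as A | 0.23 | 0.33 | 0.47 | 0 |
| E. No root intact, otherwise as A | 0 | 0 | 0 | 0 |
| F. As B, but location right in 80% | 0.68 | 0.71 | 0.74 | 0.60 |

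The last column uses roots called injured by both MRI and surgeon.

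B and F share the same intact/injured accuracy, and kappa does rise from one to the other, so it is not blind to location. But A and F cannot be told apart from the weighted value: linear 0.67 against 0.71, and quadratic 0.78 against 0.74, where the reader who guesses scores higher.

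**What a direct measure shows.** Take sensitivity and specificity for avulsion among roots injured at surgery, counting an MRI reading of intact as not avulsed.

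- A: 0.50 and 0.50.
- B: 0.9 × 0.5 = 0.45 and 1 − 0.45 = 0.55.
- F: 0.9 × 0.8 = 0.72 and 1 − 0.9 × 0.2 = 0.82.

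A reader with no location information has a sum of 1 in both A and B; F has 1.54.

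**Precision.** With 105 roots, 60% injured and half of those avulsed, there are about 31.5 avulsed roots. At a sensitivity of 0.80 the standard error is √(0.8 × 0.2 / 31.5) = 0.071, so the 95% interval is about ±0.14 if roots were independent. Positive correlation within infants would widen it.

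**The case against.** The strongest reply has four parts.

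First, a reader might infer that the weighting is the cause. It is not the main one: in the base case unweighted kappa is already 0.55, and linear weights add about 0.12. Dropping the weights would not cure the problem. This stands, and it is why the remedy is a separate analysis.

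Second, a reader might take the half or three-quarter credit as what the plan will do. The plan fixes neither the weights nor the category order, and a custom matrix could remove the credit. This stands too; what is certain is that the weights are unspecified.

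Third, perfect intact/injured detection combined with no location information is an extreme case. Section 4.3.2 scores specific pre-ganglionic signs, and section 1.1 reports accurate assessment of both injury types. Where most operated roots are injured, kappa falls and exposes the failure (rows D and E). This limits the size and not the principle: masking is greatest in a pooled kappa or at levels with many intact roots.

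Fourth, this is a secondary analysis with no kappa threshold or adoption rule. A three-category kappa is a reasonable summary of level and extent, and the recorded data allow a rupture/avulsion split later. All true, but a split chosen later is not pre-specified, and location is a named part of the objective.

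**Conclusion.** The concern holds in a limited form. Section 8.4 provides no analysis that isolates pre- versus post-ganglionic agreement, and it leaves the kappa weights open. Under assumed prevalences, a reading with no location information can give a weighted kappa of 0.67 (linear) or 0.78 (quadratic); under less favourable assumptions, 0.53 and 0.62, or 0.33 and 0.47. The size depends on the share of intact roots among operated infants and on the accuracy of intact/injured calls, neither of which the documents give.

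The documents do not support the stronger inference that the planned kappa will look good when MRI fails on location, or that the trial would then endorse MRI for planning. Nor do they establish that the result will be a set of separate per-level kappas, since per-level or pooled reporting is not settled. The primary AUC analysis is unaffected. The change is worth making because it is cheap and the objective asks the question explicitly.

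**What to change.** In section 8.4:

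- Keep the three-category kappa as a description of level and extent. State its weight matrix and whether it is per level or pooled.
- For the location part of Secondary Objective 1, pre-specify the sensitivity and specificity of MRI for avulsion among roots found injured at surgery. Count an MRI reading of intact as not avulsed, and show those readings in the full 3×3 table.
- Optionally add, as a supplement, a rupture-versus-avulsion kappa among roots called injured by both MRI and surgeon.
- Pool over the five levels, with a 95% confidence interval from resampling infants, and give per-level tables descriptively.

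The cost is a paragraph of text and a little extra analysis; no new data, visits or subjects are needed. Pooling averages over levels that may differ, which is why the per-level tables stay. With about 21 operated infants the interval will still be fairly wide.
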